2.2 EFFECTS OF VARENICLINE ON SMOKING REDUCTION PRIOR TO THE QUIT DATE

Previous research has shown that abstinence at the end of treatment is strongly predicted by the extent to which smokers spontaneously reduce *ad libitum* smoking in the initial weeks of pharmacotherapy that is initiated before the quit-smoking date. This finding was initially discovered by the principal investigator (2009) using pre-quit date nicotine skin patch treatment and has been extended by other investigators who have found similar results using bupropion and varenicline. This early marker of subsequent success can be extremely useful in clinical practice by helping to guide adaptive changes in treatment before a potential relapse occurs. We will assess the extent of smoking reduction in participants during the initial seven days of treatment (prior to their planned quit date) through the End-Of-Study, indexed by smoking diaries and biochemical measures (expired air carbon monoxide). We will correlate these reductions with abstinence assessed at the end of treatment.

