4.8.2 All other visit Windows

Participants may attend sessions up to four-calendar day's pre or post the scheduled visit.

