8.3 Pre-Quit Session (V2)

After completion of a minimum five-day observational period, participants will come to the Center for assessment, training (including brief quit smoking counseling), and dispensing of study drugs. The quit date will be scheduled for the day after Visit 3, and seven days after commencing the study drugs. The sequence of the following assessments will be at the discretion of the Investigator or designee.

- Document concomitant disease and medication changes
- Physical examination (if indicated)
- Expired air CO breath test
- Vital signs (blood pressure, heart rate, respiratory rate)
- Weight
- Brief smoking cessation counseling (QuitAssist Counseling Handout)
- Urine pregnancy test (all females)
- Dispensing of study drugs
- Verification of proper use of the SMS messaging (refresher training, if needed)
- Questionnaires
 - Employment History
 - o FTND
 - PSS-10
 - o 6-Item STAI
 - Adverse Effects Questionnaire
 - Patient Health Questionnaire (PHQ-9)
 - Wisconsin-Predicting Patient's Relapse (WI-PREPARE)
 - Modified Cigarette Evaluation Questionnaire (mCEQ)
 - Smoking Status (daily via SMS survey, commence after visit)
 - o Medication Compliance (daily via SMS survey, commence after visit)

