8.4 Day before quit date (V3)

Six days after starting medications (one day prior to quit date), participants will return to the Center for assessment and collection/dispensing of study drugs. The sequence of the following assessments will be at the discretion of the Investigator or designee.

- Document concomitant disease and medication changes
- Physical examination (if indicated)

- Expired air CO breath test
- Vital signs (blood pressure, heart rate, respiratory rate)
- Weight
- Brief review of smoking cessation counseling (if indicated)
- Urine pregnancy test (all females)
- Collection and dispensing of study drugs
- Assess medication compliance
- Verification of proper use of the SMS messaging (refresher training, if needed)
- Questionnaires
 - o FTND
 - o PSS-10
 - o 6-Item STAI
 - Adverse Effects Questionnaire
 - Patient Health Questionnaire (PHQ-9)
 - Wisconsin-Predicting Patient's Relapse (WI-PREPARE)
 - Modified Cigarette Evaluation Questionnaire (mCEQ)
 - o Smoking Status (review with participant and continue daily via SMS survey)
 - Medication Compliance (review with participant and continue daily via SMS survey)

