8.5 Post-Quit Sessions (V4-V7)

Sessions scheduled after the quit-smoking date will be conducted at 2 weeks after the quit date and then at 4-week intervals until the end of the 12-week treatment period. The sequence of the following assessments will be at the discretion of the Investigator or designee.

- Document concomitant disease and medication changes
- Physical examination (if indicated)
- Expired air CO breath test
- Vital signs (blood pressure, heart rate, respiratory rate)
- Weight
- Brief review of smoking cessation counseling (if indicated)
- Urine pregnancy test (all females)
- Collection and dispensing of study drugs (collection only at the EOS visit)
- Assess medication compliance
- Verification of proper use of the SMS messaging (refresher training, if needed)
- Questionnaires
 - o FTND
 - o PSS-10
 - MNWS
 - o 6-Item STAI
 - o Adverse Effects Questionnaire
 - Patient Health Questionnaire (PHQ-9)
 - Smoking Status (review with participant and continue daily via SMS survey until End of Study)
 - Medication Compliance (review with participant and continue daily via SMS survey until End of Study)

8.6 6-Month Follow Up

Participants who successfully complete the study and are abstinent at the final visit (V7), will be contacted six months after the quit day utilizing an automated SMS messaging system, to ascertain their current smoking status.

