13.1 EFFICACY AND TOLERABILITY

13.1.1 Abstinence Outcomes

Abstinence at each time point will be defined by a self-report of no cigarette smoking (not even a puff) since the prior session, confirmed by an expired air CO reading of less than 5 ppm. The primary

abstinence outcome will be abstinence during weeks 8-11 post-quit date. An intent-to-treat approach will be taken in which any participants lost to follow-up after the point of randomization, or who have relapsed prior to the end of treatment (week 11 post-quit) will be counted as non-abstinent (in accordance with recent guidelines from the FDA). A secondary smoking abstinence outcome will be 7day point abstinence at 6 months post-quit, for participants who have not relapsed prior to the end of treatment. The main goal of the 6-month follow-up is to assess the persistence of therapeutic effects for those who do achieve end-of-treatment abstinence. This information will be helpful in determining the treatment duration in future Phase 3 clinical trials. The main hypothesis to be evaluated in this pilot study is that the incidence of varenicline-associated side effects, specifically nausea, will be diminished by co-administration of hydroxyzine, relative to historical benchmarks (see below). A one-tailed test of abstinence will be conducted, however, comparing the proportion of participants abstinent during weeks 8-11 to the historical benchmark of 45% abstinence, to provide evidence that abstinence is not significantly lower than it would be with varenicline alone. There is no reason to expect that abstinence rate would be reduced by hydroxyzine; if anything, abstinence would be expected to be enhanced by amelioration of varenicline-associated side effects and by potential effects of H1 antagonists to reduce nicotine reward.35

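### The week 2 (V4) abstinence window starts at V3, before the quit date, so smoking before the planned quit counts as failure and V4 abstinence is biased downward

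*Combined protocol and SAP*

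**What the plan says.** Section 13.1.1 gives one abstinence rule for all time points: "Abstinence at each time point will be defined by a self-report of no cigarette smoking (not even a puff) since the prior session". A biochemical condition is attached, in that the participant's report must be "confirmed by an expired air CO reading of less than 5 ppm".

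The visit calendar is in Section 8:

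- Section 8.3: "The quit date will be scheduled for the day after Visit 3, and seven days after commencing the study drugs".
- Section 8.4, on V3: "Six days after starting medications (one day prior to quit date), participants will return to the Center".
- Section 8.5, on V4 to V7: "Sessions scheduled after the quit-smoking date will be conducted at 2 weeks after the quit date and then at 4-week intervals".

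Section 4.8.2 adds the visit window: "Participants may attend sessions up to four-calendar day's pre or post the scheduled visit".

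The primary abstinence outcome in Section 13.1.1 covers weeks 8-11 after the quit date and is tested against a 45% benchmark. The secondary outcome is 7-day point abstinence at 6 months in those who have not relapsed by the end of treatment. Participants who relapse before week 11 count as non-abstinent, but relapse is not defined. No section starts the first post-quit window at the quit date or allows a grace period.

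**The concern.** At V5 to V7 the prior session is itself after the quit date, so the look-back covers only time when the participant should not be smoking. At V4 it does not. The prior session is V3, and participants are not asked to stop until the next day. Smoking at that stage is expected: Section 2.2 plans to measure how far it falls during the first week of treatment, before the quit date.

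One cigarette on the evening after V3 is enough to fail a rule that allows no puff. The CO reading cannot correct this, because it can overturn a claim of abstinence but cannot restore one. The rule therefore misclassifies people who did what the protocol asked, at one of the four post-quit sessions. If that misclassification were carried into the undefined relapse clause, it could also reach the main abstinence result.

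**Working it through.** The plan states no figure for V4 abstinence, so there is nothing to reproduce. The check has two parts.

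**1. The calendar.** Take the first day of study drug as day 0.

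- V3 is on day 6 (8.4) and the quit date on day 7 (8.3). V4 is on day 7 + 14 = 21 (8.5).
- On schedule, the V4 look-back is 21 - 6 = 15 days: 14 from the quit date plus the remainder of the V3 day.
- With the 4-day window (4.8.2), V3 can fall on days 2 to 10. If the quit date stays fixed at day 7, V3 lies between 7 - 2 = 5 days before it and 10 - 7 = 3 days after it.
- An early V3 therefore lengthens the pre-quit part of the V4 window. A V3 after the quit date does the opposite: the V4 window then misses up to 3 days of post-quit smoking.
- If instead the quit date always follows V3 by one day, the pre-quit part stays at the remainder of the V3 day. Section 8.3 states both anchors and does not say which governs when V3 is off schedule.

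**2. The size.** Let A be true abstinence from the quit date to V4, and s the share who smoke between V3 and the quit date. If the two are independent,

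V4 rate under the rule = A × (1 - s).

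The documents give neither A nor s. With A = 50% (assumption):

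| s (assumed) | V4 rate under the rule |
|---|---|
| 100% | 0.50 × 0 = 0% |
| 90% | 0.50 × 0.10 = 5% |
| 70% | 0.50 × 0.30 = 15% |
| 50% | 0.50 × 0.50 = 25% |

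To see which values of s are plausible, suppose smoking is Poisson over a 16-hour waking day (assumption). The share smoking nothing after V3 is then

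1 - s = exp(-cigarettes per day × (1 - reduction) × hours left / 16).

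At the entry minimum of 10 per day (4.1.1) with 8 waking hours left:

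| Pre-quit reduction | 1 - s | × 0.50 |
|---|---|---|
| none | exp(-5) = 0.7% | 0.3% |
| 50% | exp(-2.5) = 8% | 4% |
| 75% | exp(-1.25) = 29% | 14% |
| 90% | exp(-0.5) = 61% | 30% |

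With 4 hours left and a 90% reduction, 1 - s = exp(-0.25) = 78%, and the V4 rate is 39%.

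Independence matters. Section 2.2 expects that those who cut down most before the quit date are the likeliest to abstain. A positive association raises the V4 rate above A × (1 - s), to at most the smaller of A and 1 - s. With A = 50% and s = 90%, for example, the ceiling is 10% rather than 5%. With V3 on schedule the rate cannot exceed A. It equals A only if every participant abstinent from the quit date also smoked nothing after V3.

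**The case against.** The strongest reply is that little depends on V4. The primary outcome and the 45% test use weeks 8-11, the early-predictor analyses in 2.2 and 2.3 use end-of-treatment abstinence, the 6-month contact depends on abstinence at V7, and the go/no-go rule is about nausea. No test or decision is attached to the week 2 rate. In ordinary usage relapse follows a quit, so a cigarette before the quit date is not relapse. The daily SMS survey (8.8.2) records smoking day by day, so an analyst can count from the quit date anyway. All of this stands, and it limits the scope of the point.

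The reply also holds on size. A reader might infer that the definition forces V4 abstinence to near zero. The documents do not support that. The entry minimum of 10 cigarettes per day describes smoking before treatment, whereas V3 comes after six days on drug, in the very week when the protocol expects smoking to fall. Nor does the visit window work in one direction only.

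What the reply does not remove is the rule itself. It applies to each time point, V4 is one of them, and nothing in the plan starts its window at the quit date.

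**Conclusion.** The point holds in a limited form. As written, Section 13.1.1 counts smoking between V3 and the quit date as failure at V4, and with V3 on schedule this biases the week 2 abstinence rate downward. The calendar alone establishes that. The size does not follow from the documents. The figures of 0-5% (90-100% smoking in the gap) and 15-25% (50-70%) rest on an assumed true rate of 50%, on the assumed shares, and on independence.

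A reader might also infer that the primary abstinence result is wrong, or that a continuous-abstinence or time-to-relapse analysis is spoiled. Neither is supported. The V4 window ends about two weeks after the quit date, well before week 8, and the plan specifies no analysis of those two kinds. The weeks 8-11 outcome, the 45% test and the 6-month outcome would be affected only if V4 failure were taken as relapse. The plan does not say that, but by leaving relapse undefined it does not rule it out.

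**What to change.** In Section 13.1.1, replace the single look-back with: *At V4, no smoking (not even a puff) since the quit date; at V5-V7, since the prior session; each confirmed by expired air CO below 5 ppm.* Add one sentence: *Smoking before the quit date does not count as relapse.*

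Starting the V4 window at the quit date is correct whether V3 falls before or after it, so it also settles the visit-window problem for this outcome. The cost is two sentences. No new visit or data item is needed: the daily SMS survey after V2 asks about smoking each day, and Section 8.5 already has staff review smoking status with the participant at V4.

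### The visit-to-visit look-back in Section 13.1.1 cannot produce the named weeks 8-11 abstinence outcome on the Section 8.5 visit schedule

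*Combined protocol and SAP*

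**What the plan says.** Section 13.1.1 defines abstinence at each time point as "a self-report of no cigarette smoking (not even a puff) since the prior session", confirmed by expired CO below 5 ppm. It then says that the primary "abstinence outcome will be abstinence during weeks 8-11 post-quit date" and compares that proportion with a 45% benchmark. Participants lost to follow-up, or "who have relapsed prior to the end of treatment (week 11 post-quit) will be counted as non-abstinent", but the section does not define relapse. The secondary 6-month outcome is restricted to a subset, "for participants who have not relapsed prior to the end of treatment".

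Section 8.5 schedules post-quit visits "at 2 weeks after the quit date and then at 4-week intervals until the end of the 12-week treatment period". Section 8.3 fixes the quit date: "The quit date will be scheduled for the day after Visit 3, and seven days after commencing the study drugs". Section 2.1 puts the End-of-Study visit about 12 weeks after first dose, Section 5.5.1 identifies that visit as V7, and Section 4.8.2 allows 4 days either side of each scheduled visit.

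Section 8.6 chooses who is followed up on a different basis: "Participants who successfully complete the study and are abstinent at the final visit (V7), will be contacted six months after the quit day". Daily smoking data are also collected. The Section 8.5 list includes "Smoking Status (review with participant and continue daily via SMS survey until End of Study", but Section 13.1.1 does not tie the outcome to those data.

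**The concern.** A look-back to the previous visit can score weeks 8-11 only if some visit falls where that window opens. On the stated schedule none does, so the rule and the outcome it is meant to score describe different periods.

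The same participant can then be classified in two ways. Someone who smokes only between V5 and the start of the window fails V6 plus V7 but meets weeks 8-11 as named, unless the undefined relapse clause already excludes them. That clause could equally exclude someone who smokes inside the window but before V6, who would otherwise pass at V7.

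Three uses are affected: the one-tailed test against 45%, the correlations of early predictors with end-of-treatment abstinence (Sections 2.2 and 2.3), and the 6-month subset. In an open-label single-group study, an unsettled window also leaves room to fix the reading after the data are known.

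**Working it through.** **Inputs.** Dosing starts 7 days before quitting (Sections 5.2, 8.3) and lasts about 12 weeks (Sections 2.1, 5.2). The first post-quit visit is at 2 weeks, then visits are 4 weeks apart (Section 8.5). Each visit may move by 4 days (Section 4.8.2).

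**The plan's own anchor.** 12 weeks of dosing − 1 pre-quit week = week 11 post-quit. This reproduces the end of treatment stated in Section 13.1.1 and places V7 at day 84 − 7 = 77.

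**Nominal visits.** V4 = week 2. V5 = 2 + 4 = week 6 (day 42). V6 = 6 + 4 = week 10 (day 70). V7 = week 11 (day 77).

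**Named window.** If all of week 8 counts, it is days 50-77: 77 − 49 = 28 days. If it starts after eight full weeks, it is days 57-77: 77 − 56 = 21 days.

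**What the rule scores.**
- V6 plus V7: days 43-77, 77 − 42 = 35 days. Early start: 49 − 42 = 7 days, or 56 − 42 = 14 days.
- V6 alone: days 43-70, which misses week 11.
- V7 alone: days 71-77, 77 − 70 = 7 days.

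**Visit windows.** V5 falls on days 38-46. The early start of V6 plus V7 is then 49 − 46 = 3 to 49 − 38 = 11 days, or 56 − 46 = 10 to 56 − 38 = 18 days. It is never zero. V6 falls on days 66-74, so V7 alone can never reach back to day 50 or 57.

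**Position of V7.** With the quit date fixed 7 days after first dose, V7 falls on days 73-81 and V5 to V7 spans 73 − 46 = 27 to 81 − 38 = 43 days. Section 8.3 also ties the quit date to the day after V3. If it moves with V3, it falls 3-11 days after first dose. V7 is then on about days 80 − 11 = 69 to 88 − 3 = 85, and V5 to V7 spans about 69 − 46 = 23 to 85 − 38 = 47 days.

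**Direction.** It depends on where the window ends.
- If the window ends at the actual V7, V6 plus V7 can only lower the rate relative to it, because they score extra days. V7 alone can only raise it, because it scores fewer days.
- If the window ends at day 77, neither statement holds. With V7 on day 73, days 74-77 are unscored and either reading can raise the rate. With V7 on day 81, smoking only on days 78-81 fails either reading while meeting the window, so either can lower it.

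**Other ways to place the visits.**
- Strict 4-week spacing puts V7 at week 14. V7 then looks back over weeks 10-14, and V6 plus V7 over weeks 6-14; neither matches. It also overruns the 12-week treatment period and gives about 16-19 weeks per participant, against 14-16 in Section 3.4.
- Counting back from week 11 puts V6 at week 7, and V7 would then match. This contradicts Section 8.5, which counts forward from the quit date.

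**Size per participant.** 1/25 = 4 percentage points; 1/50 = 2 points. No significance level is stated for this test. If it were one-sided 5%, the exact lower-tail binomial p against 45% is 0.026 at 6/25 and 0.064 at 7/25, and 0.043 at 16/50 and 0.077 at 17/50. One participant would change the result only at those boundaries.

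**The case against.** The strongest reply is that weeks 8-11 is a period while the look-back rule is written for time points, and that the data to score the period exist. Daily SMS smoking reports run to the End of Study and are reviewed with the participant at each post-quit visit. On this view only a linking sentence is missing.

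That stands in part: the SMS data could date a lapse. But Section 13.1.1 gives one rule and does not name those data. The SMS item in Section 8.8 asks about cigarettes smoked that day, which is looser than not even a puff. Each survey closes when the next is sent (Section 4.8.3), and missing values stay missing (Section 12.4).

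The reply is also right that the stakes are limited. Section 13.1.1 makes nausea the main hypothesis, advancement depends only on nausea, and no power is given for the abstinence test.

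Three stronger inferences are tempting and not supported:
- *V7 alone scores the primary abstinence outcome.* Section 8.6 uses abstinence at V7 only to select people for 6-month contact. V6 plus V7 is the more natural reading of a multi-week outcome.
- *The error runs in a known direction.* That holds only for a window ending at the actual V7, and the documents do not say that it does.
- *The day ranges are firm.* V7's week is inferred, 12 weeks is approximate, and the quit date may move with V3.

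**Conclusion.** Wrong as written, at lower priority because abstinence is a supportive test. On the forward schedule in Section 8.5, no single or combined look-back equals weeks 8-11. V6 plus V7 nominally score 35 days against 28 or 21, starting 7 or 14 days early; the early start persists at every permitted V5 date.

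This rests on V5 and V6 being counted forward from the quit date. The 35-day figure also rests on V7 at about week 11. The early start does not depend on V7 or on whether the quit date moves with V3, since V5 is counted from the quit date.

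The number of participants reclassified, and so the total effect on the comparison with 45%, cannot be derived from the documents. A reader might infer that the decision to advance the treatment is at risk. It is not: the nausea go/no-go rules do not use abstinence.

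**What to change.** In Section 13.1.1, choose one.

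(a) Keep weeks 8-11. State the start day (50 or 57) and end the window at V7. Score it from the daily SMS smoking reports as reviewed with the participant at V6 and V7, add one dated question at those visits (when the participant last smoked, even a puff) to resolve unanswered days, and require CO below 5 ppm at both.

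(b) Keep the look-back rule and rename the outcome as abstinent from V5 to V7, noting that this is longer and stricter than the named weeks 8-11 when set against 45%.

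In both cases:
- define relapse to match the chosen window;
- use the same definition for 6-month contact in Section 8.6, the secondary outcome in Section 13.1.1, and end-of-treatment abstinence in Sections 2.2 and 2.3;
- reconcile Sections 2.1, 8.5 and 13.1.1 on the weeks of V4-V7. Four post-quit visits starting at week 2 and spaced 4 weeks apart do not fit within the 12-week treatment period.

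Cost: no new visits. Option (a) adds one question at two visits and slightly more analysis work, and its window length varies with V7 (24-32 days from day 50, or 17-25 from day 57, for V7 on days 73-81). Option (b) needs no new data but accepts a stricter outcome.

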1.1 STUDY DESIGN AND PLAN

This open-label study will evaluate hydroxyzine, a first-generation antihistamine, combined with varenicline, to help smokers abstain from smoking during a 12-week trial period by diminishing the nausea, stress, anxiety, and sleep disturbances associated with the use of varenicline and with nicotine withdrawal.

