3.1 STUDY DESIGN

This study design has been developed to hasten the identification and evaluation of promising new smoking cessation treatments. This single-group, small-scale, open-label study (N= maximum of 50) will evaluate hydroxyzine combined with varenicline. The rate of nausea reported in this study will be compared to the known nausea rates associated with varenicline alone (~30%). Interim data analysis will occur after 25 participants have reached the primary outcome. In choosing these thresholds, Monte Carlo simulations were conducted to determine the significance thresholds for both the N=25 and N=50 one-tailed binomial tests so that the overall false positive (Type I error) rate across all tests would be approximately 10%. Conversely, the overall false negative (Type II error) rate, whereby a promising treatment is discarded prematurely, would be approximately 20%. These initial results will fall into one of three categories:

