13.1.2 Side Effects / Tolerability

The hypothesis that hydroxyzine reduces the incidence of nausea, one of the most common side effects of varenicline, will be evaluated by comparison to the benchmark of 30% (20% above placebo rate of 10%) observed in clinical trials of varenicline.³⁶ Initially, 25 participants will be recruited and then the possibility of recruiting 25 more (total N=50) depending on an interim analysis, as follows:

- If 0-3 participants out of 25 (12% or less) report nausea, we would conclude the treatment is highly promising at the interim stage and go directly to an RCT (Branch 1).
- If 4-6 participants (out of 25) report the side effect, then the treatment will be deemed sufficiently promising to recruit an additional 25 participants (Branch 2). If 10 or less of the total 50 report the side effect of nausea (20% or less), a follow-up RCT would be warranted; otherwise the treatment would be deemed unpromising.
- If 7 or more out of 25 (28% or more) report the side effect of nausea in the interim analysis, then we would conclude it is futile to continue the pilot and the study would be terminated (Branch 3).

The frequency of treatment-emergent side effects (i.e., those that begin or worsen after the initiation of treatment) will be tabulated. Due to the problem of Type II error posed by significance testing numerous side effect outcomes (especially if corrections are imposed for multiple comparisons), descriptive statistical methods will instead be used, supplemented by calculation of confidence intervals and p-values as a flagging device to highlight differences worthy of further attention.³⁷ Hypothesis testing will be conducted for only two outcomes: 1) proportion of participants that withdraw from the study due to side effects; 2) overall adherence (i.e., proportion of scheduled doses taken) assessed by daily medication diaries and returned capsules.

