13.1.3 Statistical Power

Monte Carlo simulations conducted by our statistical consultant ([name]) revealed that if the combination hydroxyzine/varenicline treatment is no better than varenicline alone (null of 30% incidence of nausea is true) the following would occur:

- 3% go into Branch 1 (highly promising)
- 31% go into Branch 2 (larger pilot)

- 66% go into Branch 3 (early evidence of futility)
- Overall Type I error rate of 9%

If the new treatment yields a side effect rate of 15% (versus null of 30%) then:

- 47% go into Branch 1 (highly promising)
- 46% go into Branch 2 (larger pilot)
- 7% go into Branch 3 (futile)
- Overall power of 86%

If the new treatment yields a side effect rate no worse than placebo of 10% (versus null of 30%) then:

- 77% go into Branch 1 (highly promising)
- 22% go into Branch 2 (larger pilot)
- 1% go into Branch 3 (futile)
- Overall power of 98%

Thus, to detect a clinically important reduction in side effects (a relative reduction by at least 50%, from an incidence of 30% to 15% or less), the power exceeds 86%. The Type I error of the overall approach is 9%.

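### Abstinence is to be judged preserved because a one-tailed test against 45% is not significant; no alpha, margin or confidence bound is given, and at N=25 the test would often miss a 15-point loss

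*Combined protocol and SAP*

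**What the plan says.** Section 13.1.1 states that "A one-tailed test of abstinence will be conducted", "comparing the proportion of participants abstinent during weeks 8-11 to the historical benchmark of 45% abstinence", and gives the purpose as "to provide evidence that abstinence is not significantly lower than it would be with varenicline alone". It scores participants who are lost or who relapse before the end of treatment as not abstinent. It also says that the main hypothesis of the pilot concerns nausea, and that no reduction in abstinence is expected.

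The error rates elsewhere are for nausea. Section 3.1 says the nausea thresholds were chosen "so that the overall false positive (Type I error) rate across all tests would be approximately 10" percent, with a false negative rate of about 20%. Section 13.1.3 reports 9% type I error and 86% or 98% power for the nausea rule. Section 13.1.2 mentions confidence intervals only for tabulated side effects.

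The sample size is also set by nausea: "Initially, 25 participants will be recruited and then the possibility of recruiting 25 more (total N=50) depending on an interim analysis".

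**The concern.** A non-significant test against a fixed rate shows only that the data did not rule that rate out. The smaller the sample, the easier that is to achieve, so a plan that treats non-significance as reassurance rewards imprecision. Here the sample is 25 or 50, and no margin or bound says how large a loss the result would exclude.

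This is the plan's only comparison of abstinence with varenicline alone. Section 1.1 describes the combination as intended "to help smokers abstain from smoking during a 12-week trial period". Followed exactly, the plan could report a clearly low quit rate as evidence that hydroxyzine has done no harm to quitting, and that statement could carry into the rationale for the follow-up randomized trial of about 200.

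**Working it through.** **Inputs from the documents.** Benchmark 45%, one-tailed (13.1.1). N = 25 or 50 (13.1.2). Nausea rule (13.1.2): stop at 25 with 0-3 or with 7 or more reports; otherwise recruit to 50 and succeed with 10 or fewer.

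**Assumptions, because the plan is silent.** Exact binomial test in the lower tail (the direction follows from the stated purpose); one-sided alpha 0.025, 0.05 and 0.10; true abstinence 40% to 25%, that is, losses of 5 to 20 points; denominator 25 or 50 with losses scored as failures; the 45% treated as known without error.

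**Step 1. Reproduce the plan's own figures (nausea).** Let X be the count in the first 25 and Y the count in the next 25, both Binomial(25, p). Then P(go) = P(X ≤ 3) + Σ over x = 4, 5, 6 of P(X = x)·P(Y ≤ 10 − x).

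| Nausea rate | Branches 1 / 2 / 3, exact | P(go), exact | Plan |
|---|---|---|---|
| 30% | 3.3 / 30.7 / 65.9% | 8.6% | 9% |
| 15% | 47.1 / 45.9 / 7.0% | 86.1% | 86% |
| 10% | 76.4 / 22.7 / 1.0% | 98.5% | 98% |

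The stated figures are reproduced, allowing for Monte Carlo error. They describe nausea and say nothing about the abstinence test.

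**Step 2. How often N stays at 25.** Adding Branches 1 and 3 as stated in 13.1.3: 3 + 66 = 69% (nausea 30%), 47 + 7 = 54% (15%), 77 + 1 = 78% (10%). The part of this in which the treatment goes forward (Branch 1) is 3%, 47% and 77%.

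**Step 3. Critical counts.** c is the largest count with P(X ≤ c | n, 0.45) ≤ alpha.

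| Alpha | N=25: c (actual size) | N=50: c (actual size) |
|---|---|---|
| 0.025 | 5 (0.009) | 15 (0.022) |
| 0.05 | 6 (0.026) | 16 (0.043) |
| 0.10 | 7 (0.064) | 17 (0.077) |

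**Step 4. Chance that a real loss is non-significant.** P(non-significant | p) = 1 − P(X ≤ c | n, p).

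| True rate (loss) | N=25, alpha 0.025 / 0.05 / 0.10 | N=50, alpha 0.025 / 0.05 / 0.10 |
|---|---|---|
| 40% (5 points) | 97 / 93 / 85% | 90 / 84 / 76% |
| 35% (10 points) | 92 / 83 / 69% | 72 / 61 / 49% |
| 30% (15 points) | 81 / 66 / 49% | 43 / 32 / 22% |
| 25% (20 points) | 62 / 44 / 27% | 16 / 10 / 6% |

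An uncorrected normal approximation at alpha 0.05 rejects at 7/25 or 16/50 and misses a true 30% in 49% and 32% of trials.

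**Step 5. What a non-significant result can look like.** The one-sided 95% Clopper-Pearson lower bound is the 0.05 quantile of Beta(x, n − x + 1). The p-value is P(X ≤ x | n, 0.45).

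| Result | Rate | p | Lower bound |
|---|---|---|---|
| 8/25 | 32% | 0.134 | 17.0% |
| 18/50 | 36% | 0.127 | 24.7% |
| 11/25 | 44% | 0.543 | 27.0% |
| 22/50 | 44% | 0.502 | 32.0% |

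Under the exact test all four are non-significant at every alpha considered. Even an observed rate one point below the benchmark leaves a loss of 45 − 27 = 18 points (N=25) or 45 − 32 = 13 points (N=50) inside the bound.

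**Step 6. What excluding a 15-point loss would take (illustrative margin).** A 95% lower bound above 30% needs at least 12/25 or 21/50. If true abstinence is 45%, those counts are reached 46% and 71% of the time.

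**The case against.** The best defence is about weight. Nausea is the declared main hypothesis, no branch of the decision rule uses abstinence, and a favourable result leads to a separate randomized trial, not to a claim about quitting. Section 1.1 presents abstinence as something to be helped by reducing nausea, stress, anxiety and sleep disturbance, so tolerability is what is really being tested. All of this stands, and it limits the consequence. It does not make the planned inference valid.

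The 69%, 54% and 78% include futility stops, where reassurance about abstinence has little use. At 30% nausea almost all of the early stops are of that kind. This is fair, but at 15% and 10% nausea the treatment advances on 25 participants in 47% and 77% of runs.

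The miss rates depend on an assumed alpha, test and loss. At alpha 0.10, close to the convention used for nausea, a 15-point loss is missed 49% of the time at N=25 and 22% at N=50; at N=50 and alpha 0.05 a 20-point loss is missed only 10% of the time. Those figures belong in the account. The assumptions are needed only because the plan leaves the quantities out.

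The plan does not use the words equivalent or non-inferior. True, but it offers the result as evidence about whether abstinence is lower, and the following sentence is reassuring in tone.

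Scoring losses as failures can only lower the observed rate. That makes rejection likelier but does not reduce imprecision. Section 12.4, which uses observed values only, is not reconciled with this scoring; applied to abstinence, it would shrink the denominator.

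**Conclusion.** The concern holds. The plan treats a non-significant result as evidence that abstinence is not lower, with nothing stated about how large a loss the result could rule out. With an exact lower-tail test, a 15-point loss would go undetected in 49% to 81% of trials at N=25 and 22% to 43% at N=50, for one-sided alpha 0.10 down to 0.025. Losses of 5 to 10 points would usually go undetected at N=25; at N=50 a 5-point loss usually would, and a 10-point loss would in about half to nearly three quarters of trials. N=50 would usually detect a 20-point loss.

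The alpha, the statistic, the direction of the test and the size of loss are assumptions; the benchmark and sample sizes are the plan's. The direction does not rescue the plan: an upper-tail test for superiority over 45% would not support the stated conclusion either. The nausea decision rule is unaffected, so the point concerns the validity of one secondary conclusion. It should be corrected before the data are seen.

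**What to change.** In section 13.1.1, replace the inference from non-significance with estimation: report the weeks 8-11 abstinence rate with its exact (Clopper-Pearson) one-sided 95% lower confidence bound, and state which loss from 45% that bound excludes. If the sponsor wishes to claim that abstinence is preserved, it should name the loss to be excluded in advance; otherwise the bound should be labelled descriptive. If the test is kept, its statistic, direction and alpha should be written down. One clause should confirm that scoring losses as failures takes precedence over section 12.4 for this outcome.

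This is two or three sentences of text plus that clause, with no new data or participants. The price is a less favourable statement about quitting: on the illustrative 15-point margin, a treatment with true abstinence of 45% would meet the criterion 46% of the time at N=25 and 71% at N=50. Another interval method would also serve; what matters is that the bound, and not the absence of significance, carries the conclusion.
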